The immune system in the gut actively induces an immune tolerant state to the proteins that are normally consumed. Food allergy occurs when the body has a break in this tolerance, which results in an abnormal immune reaction to food. Peanut allergy is an immunoglobulin E (IgE)-mediated hypersensitivity reaction following the ingestion of normally innocuous peanut protein. Cross-linking of peanut-specific IgE (sIgE) bound to high affinity IgE receptors on mast cells and basophils triggers immediate degranulation. Subsequent release of a diverse array of inflammatory mediators results in severe allergic symptoms such as hives, wheezing, vomiting and, in severe cases, anaphylactic shock. Release of these mediators also initiates Type 2 T-helper cell (Th2) cytokine release, which results in eosinophil infiltration and creates a vicious cycle of chronic allergic inflammation. Like other forms of allergy immunotherapy, OIT to peanut involves a slow up-dosing of exposure to allergen, in this case peanut, over time to desensitize or increase the threshold of reactivity to peanut. Once reaching a target level of peanut protein, subjects are continued on a maintenance dose of peanut protein to maintain desensitization. Although many subjects on a maintenance dose of peanut protein have demonstrated desensitization to peanut (ie, the ability to tolerate a level of exposure to peanut without an allergic reaction), up to 80% of subjects exhibit related adverse events (AEs) during OIT, with 42% experiencing systemic reactions and 49% experiencing gastrointestinal (GI) symptoms; the majority of these are mild and decline with prolonged treatment (Virkud, 2016). Up to 20% of subjects, however, are unable to complete the up-dosing regimen due to side effects, which are primarily GI related. An additional issue with current OIT is its limited ability to induce clinical tolerance when subjects are taken off daily peanut intake (Vickery, 2014). In many of the studies with peanut OIT, despite years of immunotherapy, subjects never achieve tolerance and are re-sensitized within weeks of halting daily peanut intake, with a small percentage ($\sim 10\%$) maintaining a sustained unresponsiveness even after 3 months off OIT.

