6. STUDY DESIGN

6.1. Study Description and Duration

[figure not shown]
This is a phase 2, multicenter, randomized, double-blind, parallel-group, 2-arm study in subjects aged 6 to 17 years inclusive who are allergic to peanut. The study consists of a screening period of up to 16 weeks; a 28 to 40 week double-blind treatment period, which includes 4 weeks of pretreatment with dupilumab or placebo followed by 24 to 36 weeks of treatment with dupilumab or placebo followed by 24 to 36 weeks of treatment with dupilumab or placebo in combination with a gradual up-dosing of AR101; a 24-week maintenance phase with 300 mg/day AR101 with concomitant dupilumab or matching placebo (for subjects who achieve 300 mg/day AR101 for at least 2 weeks in the up-dosing period); and a 12-week post-treatment follow-up period (Figure 1). Subjects who do not achieve 300 mg/day will still enter the 12-week follow-up. Visit windows should be adhered to as per the schedule of events, which contains flexibility in the screening and up-dosing periods to accommodate dose reductions and re-escalation as well as COVID-19 restrictions of in-clinic visits.

All AR101 dose escalation will need to be done in-clinic. If the scheduled bi-weekly up-dosing is not possible, the up-dosing period may be extended by up to 12 weeks (optional visits 15a-f) if necessary to accommodate dose reductions and re-escalation as well as COVID-19 restrictions of in-clinic visits. If necessary, subjects may continue on a dose beyond the planned 2-week duration during the up-dosing period. If a temporary hold on up-dosing of AR101 is needed (current dose maintained), the investigator should follow up with the subjects via telephone call to evaluate safety and administration at current dose.

The duration of the study is approximately 64 to 76 weeks, excluding the screening period, for subjects who enter the maintenance period, and 40 to 52 weeks, excluding the screening period, for subjects who do not achieve 300 mg/day AR101 for at least 2 weeks at visit 16 and do not enter the maintenance period.

Figure 1: Schematic of Study Design

Enroll 2-arms (2:1), up-dose AR101 from week 4 to week 28 to 40. Subjects in DUP (dupilumab) +AR101 group will be re-randomized to DUP+AR101 and PBO (placebo) + AR101, but only those subjects who achieve 300 mg/day AR101 for at least 2 weeks will be eligible to enter the 24-week maintenance treatment. Subjects who do not achieve 300 mg/day AR101 will enter a 12-week follow-up

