6.1.1. Description of AR101 Dose Escalation, and Study Stopping Rules

6.1.1.1. AR101 Initial Dose Escalation Day at Week 4

The IDED will be done in-clinic at week 4 and consist of AR101 dosing, beginning at 0.5 mg of AR101 with graduated doses every 30 minutes up to 6 mg (cumulative 12 mg) over 5 hours (see Table 1 and Appendix 4). Subjects must be stable, with stable lung function, FEV1 >80% predicted, without evidence of wheezing on exam, or active allergic symptoms such as AD or symptoms of allergic rhinitis or any other symptoms that in the clinical judgement of the study physician contradicts initial dosing.

Trained clinical staff will be present at all times during all of the in-clinic AR101 dosing visits and will be available to respond within minutes to any allergic reaction. Allergic events (Appendix 2) will be monitored for at least 2 hours after the last dose or for at least 2 hours after resolution of symptoms prior to discharge from the clinic. Subjects tolerating the escalation dose will continue to administer a 3 mg/day dose at home for the next 14 days. Subjects who do not tolerate the 6 mg single dose (12 mg cumulative) during IDED, due to moderate or severe allergic reactions

(Appendix 4), will be considered treatment failures and will not initiate home AR101 dosing and should be early terminated from the study.

6.1.1.2. AR101 Up-Dosing Regimen Starting at Week 6

Subjects in the placebo and dupilumab treatment groups will have bi-weekly in-clinic visits with bi-weekly dose increases of the daily oral home AR101 dose from 3 mg/day up to a maximum of 300 mg/day by week 24 to 36 (see Table 2) depending on safety (see Appendix 5). Subjects who exhibit moderate symptoms (Appendix 2) may have the dose reduced by 1 dose level per visit (ie, go back to the previous dose prior to new up-dose) until dose tolerated with no or mild symptoms (see Appendix 5). A dose reduction, at the investigator's discretion, may also be implemented for an intercurrent adverse event. Subjects who exhibit severe allergic symptoms (Appendix 2) must be discontinued from study drug (see Appendix 5).

Note: As of Amendment 3, the up-dosing period has been extended to accommodate dose reductions and re-escalation as well as COVID-19 restrictions of in-clinic visits. This extension permits a maximum up-dosing period of 40 weeks, while 28 weeks is ideal (consisting of 4 weeks pretreatment, 22 to 34 weeks of up-dosing, and at least 2 weeks at the maximum dose.)

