Proportion of subjects who reach 300 mg/day dose of AR101 by visit 16 will be analyzed using the Cochran-Mantel-Haenszel test adjusted by randomization stratification factors to assess the treatment difference in the proportion of subjects who reach the 300 mg/day dose of AR101 in the FAS. The proportion of subjects who reach the 300 mg/day dose of AR101 and its 95% confidence interval will be calculated for each treatment group with Clopper-Pearson confidence limits. Estimate of treatment difference, p-value, and the 2-sided 95% confidence interval using normal approximation will be provided.

Time-to-event Endpoint at visit 16

Time from randomization to the first time when subjects reach 300 mg/day dose of AR101 during the 28 to 40-week treatment period will be analyzed using the Cox proportional hazards model including treatment and randomization strata as factors. The hazards ratio, its 95% confidence interval and p-value will be reported. The Kaplan-Meier plots will be provided.

Continuous Endpoints at visit 22 and visit 25

Change in cumulative tolerated dose (log transformed) of peanut protein during a DBPCFC from baseline to visit 22 in subjects (continuously) treated with dupilumab plus AR101 vs placebo plus AR101, and change in cumulative tolerated dose (log transformed) of peanut protein during a DBPCFC from baseline to visit 22 in subjects (previously) treated with dupilumab plus AR101 (and re-randomized to placebo plus AR101) vs placebo plus AR101, will be assessed in a similar fashion as in visit 16 including missing data imputation and sensitivity analysis.

Percent change from baseline to visit 22 and visit 25 in peanut-specific IgE in subjects continuously treated with dupilumab + AR101 vs placebo + AR101 will be analyzed in a similar fashion as in visit 16.

Binary Endpoints at visit 22

Proportion of subjects (continuously) treated with dupilumab + AR101 vs placebo + AR10, and proportion of subjects (previously) treated with dupilumab + AR101 and re-randomized to placebo + AR101 vs placebo + AR101, who 'pass' a post-maintenance DBPCFC with 2044 mg cumulative peanut protein at visit 22 will be assessed the same way as for visit 16 including missing data imputation and sensitivity analysis.

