5.7.2. Analysis of Adverse Events of Special Interest

The adverse events of special interest (AESI) for dupilumab and AR101 will be summarized by AESI category (see Section 10.4) and HLT/PT, respectively.

The time to first AESIs (TEAE by category) or TEAE leading to permanent treatment discontinuation will be assessed by Kaplan-Meier estimates. Kaplan-Meier plots will be provided. In order to detect any safety signals, the hazard ratio (HR) will be provided together with the corresponding 95% confidence interval (CI) for the selected adverse events. Hazard ratios will be calculated using a Cox model including factors of treatment group, and randomization strata. The time is defined as the date of first event – the date of first dose + 1. Subjects without an event will be censored at the end of each study period. Graphs of cumulative incidence rate over time will be presented by treatment group.

The number of anaphylactic reactions, the number and percent of subjects experiencing an anaphylactic reaction, the number and percent of subjects experiencing an anaphylactic reaction by maximum severity using the Muraro Grading Scale (Muraro 2007), the number of subjects experiencing an anaphylactic reaction was an SAE, the number of subjects experiencing an anaphylactic reaction that required use of epinephrine will be summarized for each study period and during DBPCFCs.

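### The SAP does not say how subjects who stop AR101 before reaching 300 mg/day enter the time-to-300-mg analysis, and the hazard ratio depends on that choice

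*SAP*

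**What the plan says.** - **Analysis.** Under SAP 5.6.2, time from randomization to first 300 mg/day "will be analyzed using the Cox proportional hazards model including treatment and randomization strata as factors", with Kaplan-Meier plots. No censoring rule is given for this endpoint. SAP 10.1 lists the mFAS and FAS for it and no supportive or sensitivity analysis.
- **Earliest event.** Protocol 6.1.1.2 raises the daily dose "up to a maximum of 300 mg/day by week 24 to 36". Its Table 2 first shows 300 mg at week 24. Protocol 6.1 adds: "All AR101 dose escalation will need to be done in-clinic".
- **Earliest stop.** Subjects who do not tolerate the week 4 escalation day "will be considered treatment failures and will not initiate home AR101 dosing" (Protocol 6.1.1.1). Protocol 6.1.1.2 says: "Subjects who exhibit severe allergic symptoms (Appendix 2) must be discontinued from study drug". Missing more than 7 consecutive days of AR101 is also a stopping rule (6.1.2.3). Stopping either product permanently stops the other (8.3.2).
- **Expected frequency.** Protocol 1 says: "Up to 20% of subjects, however, are unable to complete the up-dosing regimen due to side effects".
- **Nearest censoring rule.** SAP 5.7.2, for adverse events of special interest, says: "Subjects without an event will be censored at the end of each study period". SAP 3.3 ends the up-dosing period at the early termination visit for subjects who do not complete dosing to visit 16.
- **Analysis set.** SAP 5.6 makes the mFAS primary for all efficacy endpoints at visit 16. SAP 3.1 limits the mFAS to subjects who had the week 28 food challenge, and SAP 2.4 offers that challenge only to subjects who have been at 300 mg/day for at least 2 weeks.

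**The concern.** A subject who permanently stops AR101 cannot later reach 300 mg/day. Discontinuation is therefore a competing event, and censoring at that point is not neutral. The schedule makes this sharper than usual because there are about 20 weeks (week 4 to week 24) in which subjects can fail and none can succeed.

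The protocol's background data place the trouble in that interval. Section 3.2.1 says that most adverse events occur in the first 12 weeks. Section 3.2.3.2 says that most allergic side effects occur below 100 mg/day, which by Table 2 means before week 16.

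Preventing up-dosing failure is one of the main ways dupilumab could help. Depending on a rule that the SAP leaves open, this endpoint either reflects that benefit or is blind to it.

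**Working it through.** **Figures in the plan.** The documents give no event count, hazard ratio or power for this endpoint. The one power statement, 80% for the primary endpoint (40% against 65%, 104 and 52 subjects, Fisher exact, two-sided 5%), reproduces as 81.1% by exact enumeration. It does not bear on this point beyond fixing the sample size.

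**Inputs from the documents.** 104 dupilumab and 52 placebo subjects; first event at week 24; dose steps every 2 weeks; stopping possible from week 4; up-dosing window to week 40; up to 20% not completing up-dosing.

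**Assumptions.** Stopping shares by arm. Stops spread evenly over weeks 4 to 24. The same up-dosing speed in both arms for those who continue, with probability q of reaching 300 mg/day at each 2-weekly visit from week 24 (q = 0.6 or 0.9).

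**Hand check, 20% against 10%, q = 0.6.**
1. Early stoppers: placebo 52 × 0.20 = 10.4, leaving 41.6; dupilumab 104 × 0.10 = 10.4, leaving 93.6.
2. Expected events at week 24: placebo 41.6 × 0.6 = 24.96; dupilumab 93.6 × 0.6 = 56.16.
3. Stoppers censored at stopping: 24.96/41.6 = 0.60 and 56.16/93.6 = 0.60. The ratio is 1.00, and it would be 1.00 for any stopping shares.
4. Stoppers kept at risk: 24.96/52 = 0.48 and 56.16/104 = 0.54. The ratio is 1.125.
5. Week 26, stoppers kept at risk. Events are 41.6 × 0.4 × 0.6 = 9.98 and 93.6 × 0.4 × 0.6 = 22.46. At risk are 52 − 24.96 = 27.04 and 104 − 56.16 = 47.84. Hazards are 0.369 and 0.470, ratio 1.27. The ratio rises over time as stoppers become a larger part of the risk set.

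**Simulation.** 600 trials per scenario and per value of q; Cox model with treatment only and Efron ties. Ranges are over the two values of q. The last column is an unstratified normal-approximation test of the proportion reaching 300 mg/day, not the planned CMH test.

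| Early stopping, placebo vs dupilumab | HR, censored at stopping | HR, at risk to week 40 | Rejection rate, at risk to week 40 | Rejection rate, proportion |
|---|---|---|---|---|
| 20% vs 20% | 0.99 | 1.00 | 3–6% | 5–7% |
| 20% vs 10% | 0.99 | 1.29–1.30 | 26% | 41–42% |
| 20% vs 5% | 0.99–1.00 | 1.53–1.54 | 61–63% | 81–83% |
| 20% vs 0% | 0.99 | 1.90 | 94% | 100% |
| 30% vs 10% | 0.99 | 1.67–1.68 | 75–77% | 86–88% |

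With censoring at stopping, the rejection rate is between 1% and 6% in every row.

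**Kaplan-Meier.** Let s be the share stopping before week 24 and c the share of the remainder who reach 300 mg/day. The true proportion is (1 − s)c. With stoppers censored, and no one else censored, one minus Kaplan-Meier ends at c. The overstatement factor is 1/(1 − s); for s = 0.20 it is 1/0.80 = 1.25. In the simulation almost every continuing subject reaches the dose, so the placebo curve ends near 100% while the true value is 80%.

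**Analysis set.** Under SAP 3.1 with SAP 2.4, every mFAS subject has already reached 300 mg/day, so up-dosing failures are absent by construction. SAP 2.3 and Protocol 11.3.1 instead count subjects who discontinue before week 28 in the primary set. The two definitions conflict.

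**The case against.** The strongest reply is that the SAP names a model, not a censoring date. The endpoint runs up to visit 16, and Protocol 8.3.2 asks subjects who stop drug but stay in the study to attend the remaining visits. Censoring non-achievers at the end of the window is therefore compatible with the text. This stands. A reader might infer that the plan removes every early stopper and ignores up-dosing failure, but the documents do not support that. The SAP states no rule here, the early termination date is only an analogy from SAP 5.7.2 and 3.3, and slow up-dosers and those who stop after week 24 remain at risk under either rule.

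Second, with equal speed in both arms a hazard ratio of 1.0 is the right answer to the question of speed, and Protocol 3.2.1 raises faster up-dosing separately from drop-out. This also stands. Preferring the other ratio is a choice of estimand, so the two should be shown together.

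Third, failure is assessed elsewhere. SAP 5.6.2 has a CMH test of the proportion reaching 300 mg/day in the FAS, SAP 2.4 counts subjects not at 300 mg/day for 2 weeks as food challenge non-responders, and SAP 5.4 and 5.7.2 plan time-to-withdrawal and time-to-discontinuation displays. The proportion test is in fact the more sensitive to early failure (41–42% against 26% in the 20% vs 10% case). This limits the harm. It does not tell a reader what the hazard ratio means, and it does not correct a Kaplan-Meier plot drawn with stoppers censored.

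Finally, a reader might infer that the plot will show nearly everyone reaching 300 mg/day. That needs both censoring at stopping and c close to 1, and the documents establish neither.

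**Conclusion.** The gap is real and worth closing before unblinding. The SAP does not define how subjects who stop AR101 before 300 mg/day enter this analysis, and the answer changes the result: about 1.0 or about 1.3 for assumed stopping of 20% against 10%, and 0.99 or 1.90 for 20% against 0%, from the same data.

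That nobody who stops before week 24 enters a risk set when censored at stopping follows from the schedule and does not depend on the assumed rates. The sizes do depend on them: the documents give only up to 20% overall, and the split by arm, the timing of stops and the equal speed are assumptions. The mFAS as SAP 3.1 defines it removes up-dosing failures whatever censoring rule is chosen.

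The endpoint is outside the hierarchy in SAP 5.6.3, so the primary conclusion is untouched. At stake is the interpretation of one secondary endpoint.

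**What to change.** In SAP 5.6.2 and 10.1, for time to first 300 mg/day:
1. Make the FAS the lead analysis set, and reconcile the mFAS definition in SAP 3.1 with SAP 2.3 and Protocol 11.3.1.
2. Define permanent AR101 discontinuation before 300 mg/day as a competing event.
3. Show cumulative incidence curves by arm in place of Kaplan-Meier plots.
4. Report the hazard ratio with discontinuers kept at risk as non-achievers to the end of the up-dosing window (week 40 plus the visit window).
5. Report the cause-specific hazard ratio beside it, labelled as speed among subjects still up-dosing.

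The cost is a short SAP edit and no new data. The downside is that the ratio in item 4 mixes speed with failure and, as the hand check shows, need not be constant over time. It should be read with the curves and with the FAS proportion endpoint.

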2.2. Secondary Objectives

- To assess whether dupilumab as adjunct to AR101 compared to placebo improves desensitization at the completion of up-dosing, defined as an increase in the cumulative tolerated dose (log transformed) of peanut protein during a post up-dosing DBPCFC at visit 16
- To assess whether dupilumab as (indefinite [continuously]) adjunct to AR101 compared to placebo maintains desensitization, defined as an increase in the proportion of subjects who pass a post maintenance DBPCFC at visit 22
- To assess whether dupilumab as (limited [previously]) adjunct to AR101 compared to placebo maintains desensitization, defined as an increase in the proportion of subjects who pass a post maintenance DBPCFC at visit 22
- To evaluate the safety and tolerability of dupilumab as adjunct to AR101 compared to placebo
- To assess the effect of dupilumab (compared to placebo) as adjunct to AR101 on the change in peanut-specific IgE, IgG, IgG4, and peanut-specific IgG4/IgE ratio
- To assess if dupilumab increases the tolerability of AR101 as measured by the daily symptoms (electronic diary [e-diary]) during the up-dosing phase

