3.2.2. Rationale for Study Design

AR101, with and without dupilumab, will be tested in a 2-arm, double-blind, randomized, parallel-group study in subjects with confirmed peanut allergy. Pediatric subjects will be enrolled as children represent the majority of subjects with peanut allergy and are a greater risk for accidental ingestion of peanut. Dupilumab/placebo treatment for 28 to 40 weeks as an adjunct to 24 to 36 weeks of daily AR101 treatment will be evaluated, followed by maintenance period of 24 weeks of daily AR101 treatment with concomitant dupilumab or placebo. Two treatment groups are required to provide informative controls and minimize bias on clinical endpoints: dupilumab plus AR101 and placebo plus AR101. Subjects will be treated for 28 to 40 weeks with either Q2W subcutaneous (SC) dupilumab or placebo. After the first 4 weeks of pretreatment, subjects will begin a 24 to 36 week up-dosing regimen of daily oral AR101. The study will assess an up-dosing regimen up to a maximum of 300 mg/day over the following 24 to 36 weeks of the study. If the scheduled bi-weekly up-dosing is not possible, the up-dosing period may be extended by up to 12 weeks (optional visits 15a-f) if necessary to accommodate dose reductions and reescalation as well as COVID-19 restrictions of in-clinic visits. Thus, the up-dosing period will end at week 28 to 40 (including 4 weeks pretreatment, 22 to 34 weeks of flexible up-dosing, and at least 2 weeks at the maximum dose).

Subjects who achieve 300 mg daily dose of AR101 for at least 2 weeks at visit 16 (ie, the end of the up-dosing period, week 28 to 40) will enter a 24-week maintenance period. Subjects treated with dupilumab during the up-dosing period and who achieve 300 mg/day AR101 for at least 2 weeks will be re-randomized to 2 groups, AR101 plus dupilumab (indefinite [continuously]) and AR101 plus placebo (limited [previously]); this will allow an assessment of a lasting or limited effect of dupilumab. Subjects treated with placebo during the up-dosing period and who achieve 300 mg daily AR101 for at least 2 weeks will continue to be treated with placebo plus AR101 during the maintenance period.

This design allows for a direct comparison between adjunct dupilumab plus AR101 to placebo plus AR101 during the 28 to 40 week double-blind treatment period. It will also evaluate the effect of dupilumab in maintaining the response to AR101, defined as an increase in the proportion of subjects who pass a DBPCFC.

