4.2. Secondary Endpoints

• Change in the cumulative tolerated dose (log transformed) of peanut protein during a DBPCFC from baseline to visit 16 in subjects treated with dupilumab plus AR101 vs placebo plus AR101

NOTE: Due to the positive skew for the distribution of the "cumulative amount of peanut protein", a log transformation will be applied to reduce the skewness

- Proportion of subjects treated with dupilumab plus AR101 vs placebo plus AR101 who reach the 300 mg/day dose of AR101 by visit 16
- Time from randomization to the first time when subjects reach the 300 mg/day dose of AR101 during the up-dosing treatment phase (up to visit 16)
- Proportion of subjects (continuously) treated with dupilumab plus AR101 vs placebo plus AR101 who "pass" a post maintenance DBPCFC with 2044 mg (cumulative) peanut protein at visit 22
- Change in the cumulative tolerated dose (log transformed) of peanut protein during a DBPCFC from baseline to visit 22 in subjects (continuously) treated with dupilumab plus AR101 vs placebo plus AR101
- Proportion of subjects (previously) treated with dupilumab plus AR101 (and rerandomized to placebo plus AR101) vs placebo plus AR101 who "pass" a post maintenance DBPCFC with 2044 mg (cumulative) peanut protein at visit 22
- Change in the cumulative tolerated dose (log transformed) of peanut protein during a DBPCFC from baseline to visit 22 in subjects (previously) treated with dupilumab plus AR101 (and re-randomized to placebo plus AR101) vs placebo plus AR101
- Percent change from baseline to visit 16 in peanut-specific IgE in subjects treated with dupilumab plus AR101 vs subjects treated placebo plus AR101
- Percent change from baseline to visit 22 in peanut-specific IgE in subjects (continuously) treated with dupilumab plus AR101 vs subjects treated placebo plus AR101
- Percent change from baseline to the end of the study visit 25 in peanut-specific IgE in subjects (continuously) treated with dupilumab plus AR101 vs subjects treated placebo plus AR101

• Proportion of subjects experiencing allergic symptoms by treatment group during the up-dosing phase, mean severity score for each symptom by treatment during up-dosing phase, maximum severity score for each symptom by treatment during up-dosing phase, and difference in mean/median duration of symptoms by treatment group during up-dosing phase (all endpoints measured by the daily symptom e-diary)

CONFIDENTIAL

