2.3. Sample Size and Power Considerations

It is assumed that the proportion of subjects who achieve a cumulative dose of 2044 mg of peanut protein during a post up-dosing DBPCFC at visit 16 in placebo plus AR101 arm will be 40%, based on an Aimmune presentation at the 2018 American Academy of Allergy, Asthma & Immunology–World Allergy Organization Joint Congress; with the proportion of subjects in dupilumab plus AR101 arm assumed to be 65%, which is considered to be clinical meaningful benefit by adding on dupilumab treatment. A sample size of approximately 156 subjects (104 in dupilumab plus AR101 and 52 in placebo plus AR101) will have 80% power to detect the treatment difference of 25% between placebo plus AR101 and dupilumab plus AR101 at the 2-sided 5% significance level (the minimum significant difference is approximately 17.8%). The sample size calculations were done by Fisher exact test using nQuery (7.0).

[figure not shown]
Approximately 122 subjects who undergo the post up-dosing DBPCFC at Week 28 (visit 16 with a window of -7/+30 days) as per protocol or discontinue from study prior to Week 28 (visit 16 with a window of -7/+30 days) will be included in the primary efficacy analysis. These subjects receive AR101 dose escalation per the original protocol's 24-week up-dosing schedule. The minimum significant difference with approximately 122 subjects is approximately 20.7% between placebo plus AR101 and dupilumab plus AR101 assuming placebo plus AR101 treatment effect is 40% at the 2-sided Fisher exact test with 5% significance level.

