5.11. Analysis of Biomarker Data

All biomarker analyses will be performed on the mFAS and FAS-maintenance using all observed data. Descriptive statistics for the observed values, change from baseline and percent change from baseline values by treatment and visit will be provided for the biomarker variables as described in Section 4.9.

The Wilcoxon signed-rank test will be used to test if the change or percentage change from baseline value is significantly different from zero. P-value will be reported.

For up-dosing period, exploratory analyses for the difference between dupilumab + AR101 group and placebo + AR101 group on the change from baseline and percent change from baseline values will be performed using a rank-based ANCOVA model with treatment group and randomization stratification factors as fixed factors, and the relevant baseline values as covariate. Missing value will be imputed by LOCF method using available post-baseline data for visits up to visit 16. Pvalue for difference between dupilumab +AR101 and placebo + AR101 will be provided.

For maintenance period, exploratory analyses for the difference between continuously on dupilumab + AR101 group and continuously on placebo + AR101 group on the change from baseline and percent change from baseline values will be performed using a rank-based ANCOVA model with treatment group and randomization stratification factors as fixed factors, and the relevant baseline values as covariate. Missing value will be imputed by LOCF method using available post-baseline data for visits up to visit 22. P-value for difference between continuously on dupilumab + AR101 and continuously on placebo + AR101 will be provided.

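### The plan re-randomises dupilumab subjects to continue or stop but specifies no continued-minus-stopped estimate, so the added value of continuing must be inferred from two separate placebo comparisons

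*SAP*

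**What the plan says.** Protocol 3.2.2 gives the reason for splitting the dupilumab group after up-dosing into continued and stopped arms: "this will allow an assessment of a lasting or limited effect of dupilumab". Protocol 8.5 makes the re-randomisation 1:1, stratified by whether 300 mg/day was held for at least 2 weeks. Subjects who did not reach that dose are also re-randomised, so that they have a hypothetical maintenance assignment for an intention-to-treat analysis at visit 22.

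Both maintenance objectives in Protocol 2.2 compare dupilumab with placebo; for each, the aim is that dupilumab "maintains desensitization, defined as an increase in the proportion of subjects who pass a post maintenance DBPCFC at visit 22". The endpoints follow suit. For the continued group, Protocol 4.2 has "Proportion of subjects (continuously) treated with dupilumab plus AR101 vs placebo plus AR101 who 'pass' a post maintenance DBPCFC". For the stopped group, SAP 5.6.2 has "proportion of subjects (previously) treated with dupilumab + AR101 and re-randomized to placebo + AR101 vs placebo + AR101". The log cumulative tolerated dose endpoints use the same two pairings. The maintenance biomarker model in SAP 5.11 covers only the continued group: "exploratory analyses for the difference between continuously on dupilumab + AR101 group and continuously on placebo + AR101 group".

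SAP 3.1 makes FAS-maintenance (subjects at 300 mg/day for at least 2 weeks) the primary set at visit 22. SAP 5.6.2 carries the visit 16 methods over to visit 22, and those methods report p-values and intervals. SAP 5.6.3 sets no formal hypothesis for the maintenance phase. SAP 5 and Protocol 11.4 summarise the three maintenance groups side by side.

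**The concern.** The second randomisation creates one comparison of its own: continued against stopped dupilumab, among children who all received dupilumab during up-dosing. In FAS-maintenance, that comparison is between groups randomised at the start of the phase and stratified on reaching the dose. The two placebo comparisons are less well protected there. Their arms were randomised at baseline and then restricted to subjects who reached 300 mg/day, which dupilumab may affect and which is itself a secondary endpoint.

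With no direct contrast specified, the added value of continuing will be read from whether one placebo comparison looks positive and the other does not. A difference in significance is not a test of a difference. The alternative is a comparison chosen after unblinding.

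**Working it through.** **1. Specified contrasts.**

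| Place | Continued vs placebo | Stopped vs placebo | Continued vs stopped |
|---|---|---|---|
| Objectives (Protocol 2.2, SAP 1.2.2) | yes | yes | no |
| Visit 22 challenge endpoints (Protocol 4.2, SAP 4.5.2) | yes | yes | no |
| Analysis, subgroups, summary table (SAP 5.6.2, 5.6.5, 10.1) | yes | yes | no |
| Peanut-specific IgE at visits 22 and 25 (SAP 4.5.2) | yes | no | no |
| Maintenance biomarker model (SAP 5.11) | yes | no | no |

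**2. The plan's own power figure.** SAP 2.3 assumes that the proportion "in placebo plus AR101 arm will be 40" per cent, takes 65% on dupilumab, and says 104 and 52 subjects "will have 80% power to detect the treatment difference of 25" points. Exact enumeration of the two-sided 5% Fisher test gives 81.1%, so the figure reproduces. It covers visit 16 only; no size or power is given for any maintenance comparison.

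**3. Group sizes.** The ceiling is 104/2 = 52 per re-randomised arm. Protocol 1 says up to 20% cannot complete up-dosing. Taking 80% entry as an assumption gives 0.80 × 52 = 41.6, about 42 per arm. For placebo, 39 is assumed (0.75 × 52). The documents give no visit 22 pass rates, so a range is used.

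**4. How often the two placebo contrasts disagree when continuing and stopping are equal.** Let y be the number of placebo passes and π(y) the chance that one dupilumab arm of 42 differs from placebo at p<0.05 (pooled two-proportion z-test) given y. Given y, the two dupilumab arms are independent, so

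P(exactly one significant) = Σ P(y) × 2π(y)[1 − π(y)].

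| True pass rate, continued = stopped | Placebo | Exactly one significant |
|---|---|---|
| 70% | 50% | 32% |
| 65% | 40% (the plan's visit 16 rates) | 31% |
| 75% | 50% | 30% |
| 60% | 50% | 18% |
| 80% | 45% | 11% |
| 85% | 50% | 9% |
| 80% | 40% | 5% |

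By symmetry, half of each figure is the pattern suggesting that continuing matters (continued significant, stopped not), for example about 15% at 75/75/50. The figure shrinks once both contrasts are almost sure to be significant; at 85/85/40 it is about 1%. With 52 in every group it is 25% at 65/65/40. In the same scenarios the direct test falsely differs in 5 to 6% of trials.

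The z-test stands in for the stratified test with imputation, so these are orders of magnitude.

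**5. Precision of the direct contrast.** With equal rates p and 42 per arm, the 95% half-width is 1.96 × √[2p(1 − p)/42]:

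- p = 0.60: 1.96 × √(0.480/42) = 0.21
- p = 0.70: 1.96 × √(0.420/42) = 0.20
- p = 0.75: 1.96 × √(0.375/42) = 0.19

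**6. Power of the direct contrast (Fisher, two-sided 5%).**

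| Continued vs stopped | 42 per arm | 52 per arm |
|---|---|---|
| 65% vs 55% | 11.8% | 14.3% |
| 65% vs 50% | 23.9% | 29.5% |
| 65% vs 40% | 59.3% | 69.6% |

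By normal approximation, 80% power needs a difference of about 30.5 points (42 per arm) or 27.5 points (52 per arm).

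**The case against.** The strongest reply is that the plan answers the questions it states. Both maintenance objectives are referenced to placebo, and the endpoints match them. Whether benefit survives stopping can fairly be read as previously treated against never treated, and that contrast is specified. Protocol 8.5 shows that the re-randomisation also serves the placebo contrasts. All of this stands. A reader might infer that the stated objectives go unanswered; the documents do not support that. The unmet purpose lies in the design rationale of Protocol 3.2.2 and concerns what continuing adds over stopping.

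A reader might also infer that the continued and stopped groups are never analysed together. That is too strong. They are tabulated side by side, so a crude difference can be derived from the reported counts. Several analyses also leave their maintenance contrasts unnamed: the visit 25 pass rate, the quality-of-life and challenge-severity endpoints (SAP 4.5.3, 5.6.4), and the Cox models for events of special interest (SAP 5.7.2). The accurate statement is that no continued-minus-stopped contrast is specified.

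The restriction to subjects who reached 300 mg/day comes from the SAP's choice of FAS-maintenance. A placebo contrast on the full analysis set would keep the original randomisation. That limits this part of the concern to the set the SAP made primary at visit 22.

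The maintenance phase carries no formal hypothesis, so no error-control claim is broken. The disagreement rates matter only if the p-values are read as yes or no, but p-values will be produced. Finally, the direct contrast has low power. That is a reason to report it as an estimate; it does not supply the missing one.

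**Conclusion.** The point holds as a gap between the design rationale and the analysis. The contrast best protected by the second randomisation has no specified estimate or interval, and the indirect route to it is unreliable. With equal true continued and stopped rates, the two placebo contrasts disagree in about 5 to 32% of trials over the tabulated scenarios, half in each direction, against about 5% false differences for the direct contrast. These figures rest on assumed numbers entering maintenance (42/42/39), assumed pass rates (60 to 85% after dupilumab, 40 to 50% on placebo) and an unstratified test.

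This is a worthwhile low-cost improvement and leaves the primary analysis untouched. A reader might go further and object that the plan's definition of maintained desensitization does not separate keeping tolerance from gaining it. The documents define the term explicitly, so that is a preference and forms no part of this point.

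**What to change.** Add to SAP 5.6.2 and 10.1, for re-randomised dupilumab subjects in FAS-maintenance, the continued-minus-stopped difference at visit 22 in (a) the pass rate at 2044 mg and (b) log cumulative tolerated dose, each with a 95% CI and adjusted for the visit 16 challenge result. That result is a legitimate covariate: under Protocol 9.1.2 both visit 16 challenge days should be completed before the maintenance injections start. Use the missing-data rules already set for visit 22. Label the analysis descriptive estimation outside the alpha hierarchy, and keep the placebo contrasts as planned. Make the change before the unblinded visit 16 analysis, so that the contrast is not chosen with results in hand.

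The cost is a short analysis and one table from data already collected, with no extra visits and no alpha. The drawback is precision: about ±19 to 21 points at 42 per arm, and about 12 to 24% power for differences of 10 to 15 points. The SAP should therefore state that an interval including zero does not show that stopping is equivalent to continuing.
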